Hypothesis 1: More participants randomized to O-BMT (vs. referral) will be engaged in BMT at 30 days.

Hypothesis 2: Reductions in opioid use (on self-report and weekly urine drug testing) will be greater among participants randomized to O-BMT (vs. referral) over 24 weeks of follow-up.

Hypothesis 3: Reductions in HIV risk behaviors will be greater among participants randomized to O-BMT (vs. referral) over 24 weeks of follow-up.

2. To test the **safety** of O-BMT by determining the frequency of buprenorphine diversion.

Hypothesis 4: Diversion of buprenorphine during the 24 weeks of follow-up will not be significantly greater among participants randomized to O-BMT (vs. referral).

3. To determine the **cost effectiveness** of O-BMT by comparing costs and health service utilization between study arms.

Hypothesis 5: O-BMT will be cost-effective according to commonly accepted thresholds.

II. Background

Most Americans with OUD remain out-of-treatment. Rates of opioid use, disorder, and overdose have skyrocketed over the past decade. In 2014, of the 2.5 million Americans in need of treatment for opioid use disorder (OUD), fewer than 490,000 were admitted to addiction treatment facilities, leaving a large treatment gap.^{1,2} Buprenorphine maintenance treatment (BMT) was approved in the United States in 2002 with the goal of improving access to treatment. BMT may be offered in diverse medical settings, addressing the stigma of attending addiction treatment programs and increasing the number of locations where opioid use disorder treatment is available;¹⁶⁻²⁰ however, despite BMT availability, 80% of those with OUD remained out of treatment in the United States through 2013.⁹ Therefore, there is a large and increasing population of out-of-treatment opioid users (approximately 1.9 million), but with thirty-eight states having more than ¾ of their opioid treatment programs operating above 80% capacity, new treatment venues will be necessary.^{21,22}

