Rationale for 2 week intervention. The goal of this intervention is to encourage BMT engagement, which we expect to increase from initiating pharmacotherapy. Drop out from BMT is most pronounced in the first week of treatment, but SEP staff will be available for psychosocial support throughout this time.^{75,79} Starting treatment at home does not increase dropout from treatment.^{67,77} After BMT initiation, linkage from community-based settings to primary care is feasible.⁸⁰ We considered continuing BMT onsite for longer than two weeks to accommodate participants who are comfortable with SEP staff but uncomfortable in traditional medical settings;^{3,4} however, there are potential benefits to transferring care. Maintaining BMT at SEPs could expose participants to cues of drug use, which may trigger opioid craving;⁸¹ transfer to a CHC may improve access to medical services (mental health counseling, HIV treatment, etc.);⁸² and segregating care of PWID outside of the traditional health care system risks entrenching “separate and unequal” care.³³

Assessment of buprenorphine diversion. We will assess buprenorphine diversion in three ways. For the first two weeks of treatment in both study arms, electronic monitors will be used enabling us to monitor medication adherence in real time. Participants will be incentivized to return electronic monitors, thereby strengthening the assertion that they did not sell or give away an entire pack. We will ask participants directly about selling their buprenorphine through sequential surveys. Audio computer-assisted self-interview technology through REDcap (see below) may reduce social desirability bias in reporting stigmatized behaviors, and prior studies of medical marijuana diversion have detected high rates of diversion through self-report.⁸³⁻⁸⁵ Additionally, all participants will have urine samples tested to confirm presence of prescribed buprenorphine.

Control: Enhanced referral to BMT. The control condition will be enhanced referral to a CHC for initiation of BMT and maintenance treatment. Similar to O-BMT, the research staff will facilitate linkage to care.

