Participants will receive an expedited appointment within 1 week of the referral and a reminder phone call the day before their appointment. If participants do not attend their first appointment at the CHC, enhanced referral procedures will be repeated as long as the request occurs within two weeks of study enrollment (in parallel with the timing of O-BMT). We will assess fidelity to these referral procedures (see below). Buprenorphine providers at the CHC will follow the same procedures for BMT initiation as provided in O-BMT: assessment for OUD and co-morbidities, instruction on starting treatment at home, weekly electronic medical adherence monitors for two weeks with 4-16 mg of buprenorphine, dose adjustment after one week, and then monthly visits. Providers at the CHC will receive instruction on study procedures before commencing the trial, and procedures will be reviewed at monthly buprenorphine provider meetings at the CHC (see Letters of Support).

Training the SEP staff. Referral to addiction treatment and psychosocial support are standard services provided by the SEPs. Prior to enrolling participants, we will enhance services by providing 3 hours of training

Principal Investigator: [name]

on BMT eligibility and procedures for making appointments and reminder phone calls. We have provided these trainings to SEP staff and peer mentors with good acceptability and fidelity to procedures.¹⁴

Methods common to all aims. We will assess for BMT engagement (at 30 days), treatment outcomes (illicit opioid use and treatment retention), HIV risk behaviors, buprenorphine diversion, programmatic costs and service utilization, and participant attitudes over the study period.

Research Visits: An RA will meet with all participants at enrollment and after 1, 2, 4, 6, 8, 12, and 24 weeks have elapsed. Research visits will occur in private at the SEP office or CHC and participants will receive a \$10 Clincard payment (weeks 1, 6) or a \$25 Clincard payment (weeks 0, 2, 4, 8, 12, 24) compensation. Interviews and urine samples will be collected at each study visit. Medical records will be extracted at the completion of the study.

Data sources and measures: A complete list of measures is presented in Table 2.

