Medical Records: We will extract medical record data from the CHC, including prescription and visit information to assess *treatment engagement* and *retention in care*. Prescription data will include information both from the electronic medical record (prescriptions) and the NY Prescription Drug Monitoring Program (medications dispensed). As mandated by law, the later source includes all controlled substances dispensed by all pharmacies in New York State. Prescription data will include medication name, strength, directions, number of pills, number of refills, date of prescription, prescriber, and date medication was filled. Visit data will include date of visit, and provider. If participants request referral to a different site for BMT or are transferred to an alternative form of OUD treatment (e.g., methadone maintenance), we will request medical records using the signed, HIPAA-compliant release for medical records.

Urine Drug Testing: All research visits will include urine collection, which will be tested for buprenorphine, opiates, oxycodone, methadone, cocaine, methamphetamine and benzodiazepines.

Table 2. Timing and delivery of intervention and study measures

Measure	Study Instrument	Assessment Period (week)									
		0	1	2	4	6	8	1	2	2	4
Urine Drug Tests											
Opioid use	Urine Drug Testing	x	x	x	x	x	x	x	x	x	x
Questionnaires											
Sociodemographic information	BHIVES Study ⁶⁶	x									
HIV Risk Behaviors	RBS ⁸⁶	x		x					x	x	
Self-reported drug use	Addiction Severity Index ⁸⁷	x			x		x	x	x	x	
Depressive Symptoms	CES-D ⁸⁸	x		x				x	x	x	
Self-efficacy	DTCQ-8 ⁸⁹	x		x				x	x	x	
Quality of Life	EQ-5D ⁹⁰	x		x	x		x	x	x	x	
Patient satisfaction	PCBSS ⁹¹			x				x			

Principal Investigator: [name]

Motivation for treatment	SOCRATES ⁷³	X		X				X	
Stigma and Discrimination	Ahern et al. ⁹²	X						X	X
Buprenorphine Diversion	MGH Medication Questionnaire			X	X		X	X	X
Non-study resource utilization	Non-Study Resources Form	X			X		X	X	
Criminal justice resource utilization	Criminal and Legal Activities Form	X			X		X	X	
PTSD symptoms	PCL-5				X		X	X	X
Traumatic reexposure	LEC-5				X		X	X	X
Medical Record Review									
Treatment engagement	-					30 days			
Retention in care	-					3 month, 6 month			

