Aim 2: Primary outcome (safety): We will use a dichotomous measure (yes/no) of **buprenorphine diversion** for all participants to determine how many sell or give away prescribed medication. We will define diversion as having at least one problem behavior over the 24 weeks: non-adherence to prescribed medication on electronic monitoring, self-reported diversion, or a urine sample consistent with diversion. Adherence will be determined weekly with Wisepill adherence for one week equaling $X/7Y$, where X = number of openings in one week and Y = number of doses prescribed per day. For the composite measure, non-adherence will be considered < 90% adherence. We will adapt the MGH Medication Questionnaire, which assesses misuse of prescribed medications, including selling medication, letting others take prescribed medication, or taking medication to get “high”. For the composite measure, self-reported diversion will be defined as an affirmative response to the question, “In the past 2 weeks, have you sold your buprenorphine to others?” We will also test each urine sample for buprenorphine, and if absent among participants prescribed BMT, the urine sample will be considered consistent with diversion. Each behavior will also be explored individually.

Aim 2: Secondary outcomes (safety): We will also report illicit buprenorphine use (i.e., buprenorphine detected in urine samples of participants who are not prescribed BMT), and determine changes in illicit buprenorphine use from baseline to study completion among participants in each study arm.

Aim 3: Primary outcome (incremental cost-effectiveness ratio, ICER): The ICER will be calculated by dividing the incremental mean cost of the O-BMT arm relative to the control arm by the incremental mean effectiveness of the O-BMT arm relative to the control arm (instruments used to measure costs and effectiveness are described in detail below). The primary economic effectiveness outcome will be the quality-adjusted life-year (QALY), a measure that incorporates both duration and health-related quality-of-life and is recommended as the primary economic effectiveness measure.⁹⁴ The QALY captures a wider range of consequences than other clinical effectiveness measures, and permits comparisons across disorders and interventions, allowing for broader economic interpretation. Also, generally accepted value thresholds have been established for QALYs, but not for clinical measures.⁹⁵

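### Diversion is claimed over 24 weeks, but the self-report item asks about only 10 of them, and weeks 12 to 22 hold no diversion measure for anyone who started treatment by about week 10

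*Combined protocol and SAP*

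**What the plan says.** Hypothesis 4 (I. Overview and Specific Aims) reads: "Diversion of buprenorphine during the 24 weeks of follow-up will not be significantly greater among participants randomized to O-BMT" compared with referral. The Aim 2 primary outcome (III. Main outcome variables) uses the same period: "We will define diversion as having at least one problem behavior over the 24 weeks". It is an ever/never composite of three components:

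- **Self-report.** A yes to "In the past 2 weeks, have you sold your buprenorphine to others". It belongs to the adapted "MGH Medication Questionnaire", whose row in Table 2 reads as weeks 2, 4, 8, 12 and 24.
- **Electronic monitor.** "For the first two weeks of treatment in both study arms, electronic monitors will be used" (Assessment of buprenorphine diversion). A week below 90% adherence counts as diversion.
- **Urine.** A sample without buprenorphine while the participant is prescribed it counts as diversion. Samples are taken at research visits, which are held "at enrollment and after 1, 2, 4, 6, 8, 12, and 24 weeks have elapsed".

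Two statements of the interview schedule disagree. The Research Visits paragraph has interviews and urine at every visit. The Participant compensation paragraph makes weeks 1 and 6 urine-only, which agrees with Table 2. Hypothesis 2 also calls urine testing weekly, which the visit schedule does not provide.

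**The concern.** The outcome is defined over 24 weeks, but no component observes 24 weeks. A participant who sells only in, say, weeks 13 to 21 and answers every question truthfully says no each time.

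Two uses of the result are affected. First, D.10 Power analysis concedes that the non-inferiority comparison is weak and justifies Aim 2 by the estimate of diversion frequency it will give in the O-BMT arm. An undercount damages that fallback purpose whatever happens to the comparison. The plan also reports each behaviour separately, where the other components cannot compensate. Second, missed events can move the arm difference used for Hypothesis 4. If the interim check against 30% diversion uses the same measure, it inherits the gap.

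**Working it through.** **1. The plan's own Aim 2 figure.** D.10 Power analysis states 80% power at a margin of 10-14% with N = 250 and diversion of 10-25%. With 125 per arm and no true difference, the Wald form is margin = (z for alpha + z for power) × √(2p(1−p)/125).
- One-sided 5%: (1.645 + 0.842) × 0.0379 = 9.4% at p = 10%, and 2.487 × 0.0548 = 13.6% at p = 25%. The score (Farrington-Manning) form gives 9.8% and 13.7%. The stated range reproduces.
- One-sided 2.5%, as the planned 95% interval implies: 10.6% and 15.3% (Wald).

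The plan gives no figure for time coverage. Steps 2 to 5 derive one.

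**2. Self-report coverage, Table 2 schedule.** Windows are weeks 0-2, 2-4, 6-8, 10-12 and 22-24: 5 × 2 = 10 weeks, and 10/24 = 42%. Unasked: 4-6, 8-10 and 12-22, which is 2 + 2 + 10 = 14 weeks (58%). A participant who starts at week 2 keeps all 14 unasked weeks but has only 8 asked weeks on treatment.

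**3. Self-report coverage if interviews occur at all seven follow-up visits.** Windows ending at weeks 1, 2, 4, 6, 8, 12 and 24 cover 0-8, 10-12 and 22-24 = 12 weeks. Unasked: 8-10 and 12-22 = 12 weeks. The 12-22 gap is the same under both schedules.

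**4. The other components in weeks 12-22.** There is no research visit, so no scheduled urine. Monitor data end two weeks after treatment starts, so a start by about week 10 leaves none after week 12. Only a later starter has monitor data there.

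**5. Who the question misses.** Assume truthful answers and selling in k randomly chosen weeks of the 24. Then P(missed) = C(14,k)/C(24,k).
- k = 1: 14/24 = 58%
- k = 2: (14 × 13)/(24 × 23) = 33%
- k = 4: 9%
- k = 8: 0.4%

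**6. Direction for Hypothesis 4.** Let success mean that the upper 95% bound is below 5%. With observed rates equal to true rate × detection, P(success) = Φ((0.05 − d)/SE − 1.96), where d is the observed difference and SE = √(r₁(1−r₁)/125 + r₂(1−r₂)/125). Detection rates are assumptions. Example: true 10% vs 15% at 60% detection gives 6% vs 9%, d = 0.03, SE = 0.0333, and Φ(0.601 − 1.96) = 8.7%.

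| True rates, referral vs O-BMT | Detection 100% | 60%, both arms | 42%, both arms |
|---|---|---|---|
| 10% vs 10% | 26.0% | 38.4% | 50.7% |
| 25% vs 25% | 14.8% | 19.7% | 25.3% |
| 10% vs 15% | 2.5% | 8.7% | 17.8% |

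With unequal detection, 60% in referral and 80% in O-BMT at a true 25% vs 25%, the observed rates are 15% vs 20% and the chance falls from 14.8% to 2.5%.

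**The case against.** The strongest reply is that self-report is one of three components of an ever/never outcome. In a once-daily week, one missed opening gives 6/7 = 85.7%, below 90%, and scores the participant for all 24 weeks; one urine sample without buprenorphine does the same. The gap therefore matters only for people with no other flag. Those components can also flag people who did not divert, so a net undercount of the composite is not established. This stands.

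A reader might infer that the gap favours declaring O-BMT safe. The documents do not support that as a general statement. It requires similar detection in both arms and an upper-bound success rule. Expedited referral appointments within one week make similar timing plausible, but actual start dates may differ, and later starts in referral would put more of that arm's exposure in the sparse period. The H4 analysis paragraph also refers to the lower bound exceeding the margin. Under that condition as printed, missed events work the other way: at 10% vs 20%, the chance of meeting it falls from 20.0% with full detection to 1.3% at 42%. That rule is a separate matter.

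A reader might also scale by 10/24, so that 15% is recorded as 6.3% and a 10-point excess as 4.2 points, inside the 5-point margin. That treats self-report as the whole composite, assumes one short episode per seller, and compares a point estimate with a margin meant for a confidence bound. Even on that scaling, 10% vs 20% becomes 4.2% vs 8.3%, with an expected upper bound of 4.2 + 1.96 × 3.05 = 10.2 points; 5% vs 15% gives 9.1 points. Both fail the margin.

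Nor is everyone who sells in weeks 12 to 22 lost: selling that continues can be caught by the week 24 question or urine, and the week 6 urine falls at the end of one unasked stretch. None of this supplies a measurement inside weeks 12 to 22 for those who started by about week 10.

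**Conclusion.** The concern holds as a mismatch between the stated and the measured period. Self-report covers 10 of 24 weeks on the Table 2 schedule and 12 of 24 if interviews occur at every visit. Weeks 12 to 22 are empty under either reading for anyone who started treatment by about week 10. The five-visit count rests on a table whose text is broken in the copy read, but the Participant compensation paragraph agrees with it.

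Self-reported selling over 24 weeks is undercounted, most for brief episodes and hardly at all for sustained selling. That weakens the frequency estimate on which the plan falls back. The effect on Hypothesis 4 is conditional: toward easier non-inferiority if detection is similar in both arms and success means an upper bound below the margin, and possibly the reverse otherwise. Its net size for the composite cannot be derived from the documents. The change is worth making because it is cheap, but it does not cure the limited power at the 5% margin: 26% at a 10% rate and 15% at 25%, with full detection.

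**What to change.** - At weeks 4, 8, 12 and 24, add an item that asks about selling since the last interview, and use it for the 24-week composite. With the week 2 question, recall intervals are 2, 2, 4, 4 and 12 weeks, which sum to 24.
- Keep the 2-week item as a sensitivity measure.
- For participants interviewed only with the 2-week item, report coverage by component: self-report 10 of 24 weeks, monitor the first two treatment weeks, urine at visit dates only. Do not describe their result as diversion throughout 24 weeks.
- Reconcile the Research Visits and Participant compensation paragraphs on whether weeks 1 and 6 include an interview.

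The cost is one extra question in an existing computer-assisted interview, with no new visits or staff. The downside is more recall error, chiefly over the 12 weeks before the last visit, and two versions of the measure if the item is added while the trial is running.

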Protocol for O-BMT. This study will build off of this infrastructure at the SEPs for clinical care by adding a trained, buprenorphine-waivered physician or physician's assistant to initiate BMT during two

Table 1. Description of study arms

	O-BMT	Waitlist
Site of initiation	SEP	CHC

Principal Investigator: [name]

[figure not shown]
Site of maintenance	CHC	CHC
Type of referral	Staff-facilitated	Staff-facilitated
Primary Outcome	Engagement	Engagement
Assessment for diversion	Wisepill Technologies medication adherence + Urine Tests + Questionnaires	Wisepill Technologies medication adherence + Urine Tests + Questionnaires

Onsite program service utilization	Provider + Transfer	Enhanced Referral
SEP = syringe exchange program; CHC = community health center		

half-day sessions weekly. Participants will be registered as CHC patients to ensure continuity of care. For example, the provider will document encounters in the CHC's electronic health record via a web-based portal and patients will be able to access medical advice during off-hours through the CHC (see Human Subjects). Participants will be prescribed BMT from the SEP and then staff members will facilitate transfer a CHC for maintenance treatment. Details are presented below and in Table 1.

Initiation. Over two weeks, participants will see the study provider twice onsite at the SEP. The first visit will include: assessment of opioid use disorder, contraindications to BMT, and co-morbidities; instructions for initiating treatment; prescription for one week of medication (buprenorphine-naloxone provided by prescription and transferred by patient to a Wisepill Technologies Medication Adherence Tracker); and planning for one week follow-up. Participants will start taking medication at home, which is safe, effective, and a standard practice.⁷⁵⁻⁷⁸ Participants will be prescribed 4-16 mg of buprenorphine daily based on their withdrawal symptoms following a standard algorithm. After one week, the study provider will make dose adjustments, provide another prescription for one week of medication (second prescription), and arrange for linkage to the CHC for maintenance BMT. The SEP staff will provide psychosocial support between visits and facilitate transfer of care to a CHC as specified in pre-intervention training.. Participants who do not pick up their second prescription within 14 days will not be eligible to repeat O-BMT procedures, but they still may be referred to the CHC for maintenance BMT.

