Aim 1: To test the effectiveness of O-BMT. *H1: more participants randomized to O-BMT (vs. control) will be engaged in BMT at 30 days.* Our primary analysis will determine the effect of the intervention (O-BMT). We will use a chi square test comparing the proportion of participants in each study arm who have an active buprenorphine prescription 30 days after enrollment. We will also conduct a multivariable logistic regression adjusting for mental illness, polysubstance use, and addiction severity.

H2: Reductions in opioid use will be greater among participants randomized to O-BMT (vs. control) over 24 weeks. We will use generalized estimating equations to compare changes in opioid use between study arms over the 24 week study period. One model will use results from urine drug tests at 1, 2, 4, 6, 8, 12, and 24 weeks. A second model will compare the mean number of days (of the prior 30 days) with self-reported opioid use at 4, 8, 12, and 24 weeks.

H3: Reductions in HIV risk behaviors will be greater among participants randomized to O-BMT (vs. referral) over 24 weeks of follow-up. We will use generalized estimating equations to compare changes in injecting risk at 2, 12, and 24 weeks.

Aim 2: To test the safety of onsite buprenorphine treatment at syringe exchange programs.

H4: Diversion of buprenorphine will not be significantly greater among participants randomized to O-BMT (vs. control). By definition, participants who are not prescribed buprenorphine will not have an opportunity to divert their medication, but we will use an intention to treat approach to maintain randomization. The risk difference

Principal Investigator: [name]

threshold margin for non-inferiority will be 5%. We will construct Wald 95% confidence intervals (CIs) for a difference in diversion rates between the two arms and examine if the lower bound of the 95% CI is greater than the threshold margin. If potential confounding factors are unbalanced and require adjustment, we will apply logistic regression and estimate the Odds Ratio (OR) and its CI, examining if the lower bound of the OR is greater than the OR converted from the risk difference.

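### The urine component of the Aim 2 diversion outcome is triggered by a prescription, not by dispensed medication, so an unfilled or lapsed prescription can count as diversion, and this probably falls mainly on the O-BMT arm

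*Combined protocol and SAP*

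**What the plan says.** Main outcome variables, Aim 2: Primary outcome (safety) defines a yes/no composite, positive on "having at least one problem behavior over the 24 weeks". The three components are electronic-monitor adherence below 90%, self-reported selling in the past two weeks, and urine. The urine rule reads: "if absent among participants prescribed BMT, the urine sample will be considered consistent with diversion". The Protection of Human Subjects section repeats the expectation that people prescribed buprenorphine will have it in their urine.

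On supply, Protocol for O-BMT (Initiation) has "buprenorphine-naloxone provided by prescription and transferred by patient to a Wisepill Technologies Medication Adherence Tracker", with treatment started at home. Obtaining the medication is therefore a separate step after the prescription is written. The same paragraph adds: "Participants who do not pick up their second prescription within 14 days will not be eligible to repeat O-BMT procedures".

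On sampling, Research Visits says: "An RA will meet with all participants at enrollment and after 1, 2, 4, 6, 8, 12, and 24 weeks". Urine is collected at each visit.

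On analysis, H4 observes that "participants who are not prescribed buprenorphine will not have an opportunity to divert their medication" and keeps all randomised participants in the comparison, with a risk-difference margin of 5%.

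Two further places matter. Medical Records says that dispensing data, including fill dates, are taken from the state prescription monitoring program. The Aim 1 secondary outcomes include the proportion who filled a prescription. Neither is used in the diversion definition.

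**The concern.** H4 accepts that a person without a prescription cannot divert. The same is true of a person whose prescription was never filled, and of a person whose dispensed supply ended well before the sample. The urine rule makes no allowance for either. The lapsed case arises if prescribed is read as ever prescribed; the unfilled case arises on any reading short of dispensed.

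The error can occur only in people who were given a prescription. Under O-BMT that happens at the first onsite visit. In the referral arm it happens only after attendance at the community health center. An intention-to-treat risk difference therefore turns a difference in access to prescriptions, which the trial is designed to create, into part of the safety result. At stake is the H4 conclusion: some of any apparent excess of diversion under O-BMT may be unfilled or lapsed prescriptions.

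**Working it through.** **Plan's own figure.** D.10 Power analysis states 80% power at margins of 10-14% for N = 250 and diversion of 10-25%. With 125 per arm, equal true rates p and SE = √[2p(1−p)/125], SE is 0.0379 (p = 10%) and 0.0548 (p = 25%).
- One-sided 0.05: margin = (1.645 + 0.842) × SE = 9.4% and 13.6%. A Farrington-Manning score calculation gives 9.8% and 13.7%. The stated range is reproduced.
- One-sided 0.025, matching a two-sided 95% interval: (1.960 + 0.842) × SE = 10.6% and 15.3%. It is not reproduced at this level.

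**Size of the artefact.** Inputs:
- Share prescribed, O-BMT: 33%, 49% or 68%. Referral: 0%, 9% or 16%. These are the engagement rates in D.10, used as a proxy because the plan gives no share prescribed.
- f: the share of prescribed participants with a negative urine because no medication was dispensed or the supply had lapsed, and **not already positive on another component**. The documents give no value. It is assumed equal in the two arms and varied.

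Artefact = f × (share prescribed in O-BMT − share prescribed in referral). Against 16% in referral, in percentage points:

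| O-BMT | f = 5% | f = 10% | f = 20% | f = 30% | f that alone gives 5 points |
|---|---|---|---|---|---|
| 33% | 0.85 | 1.7 | 3.4 | 5.1 | 0.05/0.17 = 29% |
| 49% | 1.65 | 3.3 | 6.6 | 9.9 | 0.05/0.33 = 15% |
| 68% | 2.6 | 5.2 | 10.4 | 15.6 | 0.05/0.52 = 10% |

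At f = 10% with referral at 9%, the values are 2.4, 4.0 and 5.9 points; with referral at 0%, they are 3.3, 4.9 and 6.8.

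In counts at f = 10%, the false flags in O-BMT are 0.10 × 125 × (0.33, 0.49, 0.68) = 4.1, 6.1 and 8.5. In referral they are 0.10 × 125 × 0.16 = 2.0. O-BMT carries 33/49 = 67%, 49/65 = 75% or 68/84 = 81% of them.

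**Direction.** With unequal f, the sign reverses only if f in referral exceeds f in O-BMT by more than the ratio of shares prescribed. In the least favourable pairing that ratio is 33/16 = 2.1.

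**Effect on H4.** Take the test as one-sided 0.025 at the 5-point margin, with no true difference and artefact b added to O-BMT. Power = Φ[(0.05 − b)/SE − 1.96], with SE = √{[pT(1−pT) + pC(1−pC)]/125} and pT = pC + b.
- b = 0: 26% (pC = 10%) and 15% (pC = 25%).
- b = 3.3 points: 6% and 5%.
- b = 5 points: 2.5% in both.

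**Overlap between components.** Someone who fills but does not start has no monitor openings, so adherence is below 90% in the two monitored weeks and the composite is already positive. Urine adds nothing for that person, and f excludes such cases. The adherence formula divides openings by doses prescribed, so read literally it could also score a never-filler as non-adherent. Correcting the urine rule alone would then leave that person positive.

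**The case against.** **The documents do not show that first prescriptions go unfilled.** This stands. The pick-up sentence concerns only the second prescription and is a rule on repeating procedures. The remark that "Drop out from BMT is most pronounced in the first week of treatment" concerns people already in treatment, who may hold unused doses and so could divert. A reader might infer from these that the plan itself forecasts non-filling; it does not. The rule nevertheless gives the wrong answer whenever non-filling occurs.

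**The margin may not be exceeded.** A reader might reason that nearly all O-BMT participants are prescribed, and infer an artefact clearly above 5 points. With an assumed 90% against 16%, f = 10% would give 0.10 × 0.74 = 7.4 points. The documents support neither the 90% nor any value of f, and the 16% comes from referral to methadone treatment, not from enhanced referral with an appointment within a week. Engagement is probably a low proxy for ever being prescribed, so the table is not an upper bound either.

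**The error is conservative.** With similar non-fill shares it makes O-BMT look less safe and does not produce a false claim of non-inferiority. H4 also has little power at 5 points before any artefact. Both statements are correct and lower the severity.

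**Mitigations exist.** Each behavior is to be explored individually, per-protocol analyses cover those who start treatment, and staff supervise loading of the monitors. These help interpretation but do not change the primary outcome.

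**Conclusion.** The concern holds as a defect in the outcome definition: followed literally, the urine rule counts people as diverting when they had no medication to divert. That rests on the text alone. Concentration in the O-BMT arm is an inference from the timing of prescribing and the plan's engagement rates, conditional on broadly similar non-fill shares. At an assumed f of 10% and 16% prescribed in referral, the artefact is 1.7 to 5.2 points against a 5-point margin. Whether it alone uses up the margin depends on an unknown f, which would have to be 29%, 15% or 10% in the three pairings. Cases of filling without starting are not added error.

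A reader might also infer that the artefact could trip the rule to stop above 30% diversion. The Protection of Human Subjects section does not say that the interim rule uses this composite, so the documents do not support that.

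This should be fixed before outcome data are compared by arm. It biases against non-inferiority and does not invalidate the trial.

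**What to change.** Amend the Aim 2 primary outcome definition as follows:

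1. Count a negative urine as consistent with diversion only when the prescription monitoring program shows a fill whose days' supply, plus a short pre-specified window for late visits, covers the sample date. The window matters because the first supply is seven days and the first visit falls at one week. Without it, someone who sold that supply and attended a day late would be missed.
2. State that the monitor adherence criterion applies only to weeks with dispensed medication.
3. Report negative urines without a covering fill separately by arm, as non-initiation or discontinuation. All randomised participants stay in the denominator.
4. Keep the prescription-based rule as a sensitivity analysis.

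The cost is definition wording and a merge of fill dates that are already extracted. The downside is that diversion of a supply that ran out before the window is not detected by urine, and the self-report item counts only selling, not giving away. Such missed cases would also tend to lie in the arm with more prescriptions and so would favour non-inferiority. That is why both definitions should be reported.
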